Exclusion Criteria	
 1. Coagulopathy (i.e., international normalized ratio >2.0, activated partial thromboplastin time >50 seconds or platelet count <50,000/mm³) 2. Known bleeding disorder 3. Clinically relevant bleeding as defined by the International Society on Thrombosis and Hemostasis (i.e., Hb decreased ≥2 g/dl in 24 hours, required medical or surgical intervention to restore hemostasis, or in a critical organ system [i.e., retroperitoneum, pulmonary, intracranial or central nervous system]) 4. Admitted for trauma, or neurologic or spine surgery) 5. <60 days from a clinically relevant bleeding as defined above 6. <7 days after trauma or surgery 7. Anticipated surgery within 48 hours after insertion of the CVC 8. Renal failure (i.e., creatinine clearance <30 mL/min) 9. Presence of epidural catheter 9. Currently taking an antithrombotic agent (e.g., LMWH, UFH at therapeutic doses, Coumadin or aspirin) 10. Radiologically documented DVT at the site of insertion of the CVC in the previous 6 weeks 11. Known hypersensitivity to heparin or its components, including pork products 12. History of HIT (i.e., positive serotonin release assay)

	13. Currently pregnant 14. Currently lactating 15. Prior enrollment in the study 16. Limitation of care
Treatment Plan	Eligible subjects will be randomized 1:1 to treatment or control. In subjects randomized to treatment, noxaparin will be given within the first 24 hours after CVC insertion and then every 12 hours (+/-2 hours) thereafter until removal of the CVC. Dosing will start at 0.75 mg/kg for children \leq 2 months old or 0.5 mg/kg (maximum of 30 mg) for older children and will be titrated to a target anti-Xa activity of 0.2-0.5 IU/mL. Safety assessments for bleeding will be completed daily. In subjects randomized to control, no placebo will be given.

STUDY SCHEMA

LIST OF ABBREVIATIONS

AE – adverse event
CADVT – catheter-associated deep venous thrombosis
CAT - Calibrated Automated Thrombogram
Co-I – co-investigator
CRF – case report form
CVC – central venous catheter
DSMB – data and safety monitoring board
DVT – deep venous thrombosis
EDTA – ethylenediaminetetraacetic acid
ETP – endogenous thrombin potential
FDA – Food and Drug Administration
Hb – hemoglobin
HIPAA – Health Insurance Portability and Accountability Act
HIT – heparin-induced thrombocytopenia
ICU – intensive care unit
IL – interleukin
IP – Investigational Product
IRB – institutional review board

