Another agent will not be used while enoxaparin is held. Activities related to the management of the dose of enoxaparin will be the purview of the study. However, the clinical care of the child remains with the treating physician.

Restarting the Dose

Timing for restarting treatment

1. 24 hours after coagulopathy is corrected
2. 24 hours after surgery or procedure
3. After exclusion of HIT (*i.e.*, negative serotonin release assay)

Safety Laboratory Procedures and Assessments

Complete blood count, renal function tests (BUN and creatinine), and serum aminotransferases will be done within 48 hours of enrollment and at least weekly ± 2 days, thereafter. An unexplained decrease in platelet count $<50,000/\text{mm}^3$ or by 50% of baseline value in the ICU will trigger a work up for HIT (*i.e.*, send blood for serotonin release assay). Stool occult bleed will be done if clinically indicated as determined by the local investigator.

Bleeding Assessment

Bleeding assessments will be completed by the site study team on a daily basis. The team will interview the clinical care team and review the medical records for the presence of a bleed. The Bleeding Assessment Tool (Appendix III) will be completed for each episode of bleeding. This tool contains questions regarding the site, severity and timing of bleeding.

Concomitant Medications

Antithrombotic agents, including other LMWH, UFH at therapeutic doses, Coumadin and aspirin, are not allowed during the trial.

Diet and Other Considerations

There are no dietary or food restrictions with enoxaparin

Rescue Medication and Supportive Case

In case of a clinically relevant bleed, the clinical team will decide whether blood products should be administered. Protamine may also be used to control the bleeding. For suspected HIT, serotonin release assay will be done. Aside from stopping all

heparin or heparin-related products, no other therapies are needed for HIT.

Duration of Therapy

Enoxaparin will be administered every 12±2 hours until CVC removal, or earlier if the following occur:

1. Discharge from the ICU
2. Radiologic diagnosis of CADVT
3. Start of therapeutic anticoagulation
4. Clinically relevant bleed develops
5. HIT is diagnosed
6. 28 days after insertion of the CVC

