site investigators within 15 calendar days.

A safety monitor is responsible for ongoing timely monitoring of reports of all SAEs submitted by site PIs, or other sources to ensure high-quality reporting, good clinical care and to quickly identify safety concerns. The identification of SAEs will begin when a member of the local research team reports an adverse event. The local research team will monitor each child daily for pre-defined adverse events, particularly clinically relevant bleeding. The research team will interview the clinical team and review the medical records daily for these events. The site PI or his/her designee will conduct prompt investigations of all reported adverse events, especially bleeding. All SAEs will be documented on a SAE form, entered in OnCore and communicated to the PM as soon as possible and <24 hours of the site PI knowing the event.

SAEs will be reported to the Yale Human Investigation Committee and the IRBs of the participating sites per policy.

Adverse Event Committee (AEC)

PI [name] will assemble an independent 3-member AEC composed of a pediatric hematologist (chair), a pediatric intensivist and a nurse. The responsibility of the AEC is to classify all AEs for publication and presentation purposes.

Minimizing Risks

To minimize the risk of bleeding, we will exclude children at high risk of bleeding. Enoxaparin will be held immediately and permanently after a clinically relevant bleeding event as defined by the International Society on Thrombosis and Hemostasis.⁵² Bleeding from enoxaparin can be reversed with protamine or administration of fresh frozen plasma. See section on Holding the Dose, which contains criteria for holding enoxaparin temporarily and when to restart the drug. Enoxaparin will not be replaced with another agent while the drug is on hold.

Platelet count will be monitored for the development of HIT. Enoxaparin and all heparin-related products will be held temporarily for unexplained decrease in platelet count.^{14, 53} Enoxaparin will not be restarted until the child tests negative for HIT.

Subcutaneous administration of enoxaparin may cause pain. As per local ICU practice, enoxaparin may be given through a subcutaneous catheter.

It is unlikely that the blood draws will result in anemia. Packed red blood cells can be transfused for anemia per the direction of the clinical team.

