ETP. This will be measured at the [name] Laboratory using CAT, a fully automated, computer-controlled fluorometric microplate reader and its specified software (Thrombogram Thrombinoscope Synapse, Netherlands). Calibration will be conducted with each test to guarantee correction for color of the tested plasma sample. Reagents containing 1 pM and 5 pM of tissue factor (to account for the presence of enoxaparin) plus 4 µM of phospholipid will be used to trigger the thrombin generation reaction.⁵⁹

Factor VIIIa and anti-Xa activities. These will be measured at the Clinical Laboratories at Yale-New Haven Hospital, except for anti-Xa activity that is used to titrate the enoxaparin dose in subjects in the treatment arm, which is measured locally. Factor VIIIa will be measured using a 1-stage clotting assay with the BCS XP System following the manufacturer's recommendations. To minimize variability in its measurement in our analysis for this Aim, we will centrally measure anti-Xa activity using STA® Liquid Anti-Xa assay with the fully automated STA® line analyzer.⁶⁰

IL-6 and IL-8. These will be measured at the Immune Monitoring Core Facility at Yale University using Milliplex® MAP assay kits and the Millipore Luminex 200 System. This is a bead-based system that allows analysis of up to 100 analytes per well. Samples will be analyzed using Milliplex® Analyst software (EMD Millipore Corp., Germany).

Anti-IIa and TFPI. These will be measured at the Yale Center for Clinical Investigation Core Laboratory at Yale University using commercially available ELISA kits.

OUTCOME MEASURES

The primary outcome is the presence of CADVT, defined as DVT in the site of insertion of the CVC confirmed by ultrasound <24 hours after the end of the study period.^{19, 61}

Co-I [name] will lead a 3-member outcomes adjudication committee that will blindly and independently diagnose CADVT.^{40, 41} CADVT will be diagnosed if at least 2 are present: (1) intravenous echogenic material adherent to the venous wall, (2) non-compressibility of the vein, or (3) abnormal venous Doppler.^{18, 42, 62}

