Secondary outcomes include measures of efficacy (other thromboembolic events including pulmonary embolism, and length and cost of stay in the ICU and the hospital), safety (clinically relevant bleeding, confirmed HIT and mortality), feasibility (proportion of enrolled eligible children, time to 1st dose of enoxaparin, and time to target anti-Xa activity), and compliance (proportion of missed doses, and proportion of children with ultrasound). Outcomes will be measured from insertion of the CVC. Imaging for other thromboembolic events will depend on the clinical team but all images will be centrally adjudicated for the trial. Bleeding will be monitored, recorded and classified using our bleeding assessment tool. Costs will be estimated from inpatient charges using each hospital's cost-to-charge ratio.

STATISTICAL CONSIDERATIONS

This trial is designed to inform: (1) beliefs regarding the posterior probability distribution for the prophylaxis treatment effect size, defined as the difference ($pS - pE$) of the proportion of subjects developing CADVT among those receiving the current standard of no prophylaxis (pS) vs. the proportion among those receiving the early prophylaxis (pE), (2) the decision whether to proceed to a phase 3 trial, and (3) appropriate and necessary design features of a phase 3 trial.

For Aim 1, we will use a Bayesian statistical approach for modeling and data analysis, for formulating decision rules, and for interpreting results. We will also provide analogous frequentist results for reporting purposes only. We will use our empirical results to decide between 2 hypotheses regarding the difference of proportions $\delta = pS - pE$ of subjects who develop CADVT: $\delta \leq 0$ (prophylaxis is not efficacious) vs. $\delta \geq 0.06$ (prophylaxis is efficacious).

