Please select all that apply.

Check all that apply.

- ☐ Gross Hematuria
- ☐ Bleeding Around a Urinary Catheter
- ☐ Menstrual Bleed (that required medical consultation or intervention)
- ☐ Other: _____

Skip to question 17.

Bleeding Site - Intra/Retroperitoneal

12. Intra/Retroperitoneal Bleed *

Please describe the location of the bleed.

...

Skip to question 17.

Bleeding Site - Central Nervous System**13. Central Nervous System Bleed ***

Please select all that apply.

Check all that apply.

- ☐ Epidural Bleed
- ☐ Subdural Bleed
- ☐ Subarachnoid Bleed
- ☐ Intraparenchymal Bleed
- ☐ Intraventricular Bleed
- ☐ Intraspinal Bleed (any site within the spinal column)
- ☐ Other: ...

Skip to question 17.

Bleeding Site - Eye, Ear, Nose, or Mouth**14. Eye, Ear, Nose, or Mouth Bleed ***

Please select all that apply.

Check all that apply.

- ☐ Subconjunctival Bleed
- ☐ Retinal Bleed
- ☐ Hemotympanum
- ☐ Epistaxis
- ☐ Oropharyngeal Bleed
- ☐ Other: ...

Skip to question 17.

Bleeding Site - Joint

15. Bleeding in the Joint *

Please specify which joint(s) is/are involved.

Check all that apply.

- ☐ Shoulder
- ☐ Elbow
- ☐ Wrist
- ☐ Finger
- ☐ Hip
- ☐ Knee
- ☐ Ankle
- ☐ Toe
- ☐ Other: _____

Skip to question 17.

Bleeding Site - Other (Describe)**16. Other Bleeding Site ***

Please describe the location of the bleed (if possible).

Skip to question 17.

Bleeding Severity

Please select AT LEAST one item from ONLY ONE of the bleeding severity categories below. Please select the most severe category as it applies to the bleeding event documented on this current day of admission. Remember to use a different form for another bleeding event on this same day but at a different site.

17. Major Bleeding

Please check all that apply.

Check all that apply.

- ☐ Fatal Bleeding
- ☐ Clinically Overt Bleeding with Decrease in Hgb of ≥ 2 g/dL in a 24-hr Period
- ☐ Bleed that is Intra/Retroperitoneal, Pulmonary, or Involves the CNS
- ☐ Bleeding Requiring Surgical Intervention in the Operating Room

18. Clinically Relevant Non-Major Bleeding

Please check all that apply.

Check all that apply.

- ☐ Overt Bleeding Requiring Blood Product Administration
- ☐ Bleeding that Requires Medical or Surgical Intervention NOT in the Operating Room (and Does NOT Include Menstrual Bleeding)

19. Minor Bleeding

Please check all that apply.

Check all that apply.

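### Clinically relevant bleeding is classified by a site team that knows the arm, and the plan does not say that a masked committee's category is the reported outcome

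*Combined protocol and SAP*

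**What the plan says.** - **Allocation is visible.** The Trial Summary states: "In subjects randomized to control, no placebo will be given". The Randomization section gives the reason, which is to avoid painful injections that could not benefit the child.
- **Who assesses bleeding.** Under Bleeding Assessment: "Bleeding assessments will be completed by the site study team on a daily basis". The team interviews the clinical team, reviews the records, and the tool in Appendix III is completed for each episode.
- **How it is classified.** Under Outcome Measures, clinically relevant bleeding is a secondary safety outcome, and "Bleeding will be monitored, recorded and classified using our bleeding assessment tool". No masking is mentioned.
- **The criteria.** Item 17 (Major) covers fatal bleeding, overt bleeding with a hemoglobin fall of at least 2 g/dL in 24 hours, bleeding at a critical site, and surgery in the operating room. Item 18 (clinically relevant non-major) covers blood products and "Bleeding that Requires Medical or Surgical Intervention NOT in the Operating Room". The list under Discontinuing enoxaparin has a matching intervention criterion. Neither place says which medical interventions qualify.
- **Independent classification.** An independent three-member AEC is planned: "The responsibility of the AEC is to classify all AEs for publication and presentation purposes". Its masking, and its authority over the site's tool category, are not stated.
- **Contrast with other outcomes.** A three-member committee "will blindly and independently diagnose CADVT". For other thromboembolic events, "all images will be centrally adjudicated for the trial". Sonographers and central laboratory staff are also blinded.

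**The concern.** Two things combine. The person who assigns the severity category knows the arm. And item 18 is met by a clinical action, taken by a clinician who also knows the arm. If an awareness of enoxaparin makes staff quicker to intervene, or to record an ooze as needing intervention, bleeding on enoxaparin is over-counted. If staff expect minor bleeding on an anticoagulant and discount it, the treated arm is under-counted. The plan gives no basis for saying which is more likely.

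The plan uses blinded or central review for its imaging outcomes but does not state it for bleeding. It also names two classifiers, the site tool and the AEC, without saying whose category is analyzed. With very few events expected, the descriptive safety comparison that accompanies the efficacy result rests on a handful of labels. Clinically relevant bleeding also enters the planned joint model with ETP and anti-Xa (Statistical Considerations), so the same labels are used there.

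**Working it through.** **Plan's own figure.** Minimizing Risks sets the alert to the DSMB chair at 5 events: 100 × 5.3% = 5.3, rounded to 5. This reproduces. The 5.3% equals 3.0% + 2.3%, though the text does not show that step.

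**Inputs.** 100 children randomized 1:1, so about 50 per arm (Study Population; Randomization). Rates of 0-3% without anticoagulation and 2.3% on LMWH prophylaxis (Minimizing Risks).

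**Expected events per arm**
- Control: 50 × 0 = 0, up to 50 × 0.03 = 1.5
- Treated: 50 × 0.023 = 1.15

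**Effect of one label.** 1/50 = 2 percentage points; two labels, 2/50 = 4 points. The whole background range in the protocol is 3 points wide.

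**Illustration (assumed misclassification).** The documents give no reclassification rate, so the fraction x below is an assumption. Let the true rate p be equal in both arms, and let x of the otherwise event-free treated children be recorded as clinically relevant. The apparent treated rate is p + (1 − p)x. For p = 2.3% and x = 2%: 0.023 + 0.977 × 0.02 = 0.0425. The apparent risk ratio is 0.0425/0.023 = 1.85, and the extra events are 50 × 0.0195 = 0.98. The chance of 5 or more events in total comes from the exact binomial counts of the two arms added together.

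| x | Extra treated events (p = 2.3%) | Risk ratio, p = 2.3% | P(≥5 total), p = 2.3% | Risk ratio, p = 3.0% | P(≥5 total), p = 3.0% |
|---|---|---|---|---|---|
| 0 | 0 | 1.0 | 8% | 1.0 | 18% |
| 1% | 0.5 | 1.4 | 15% | 1.3 | 27% |
| 2% | 1.0 | 1.9 | 23% | 1.7 | 37% |
| 3% | 1.5 | 2.3 | 32% | 2.0 | 46% |
| 5% | 2.4 | 3.1 | 52% | 2.6 | 64% |

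Under-calling works the other way. If half of true treated bleeds were scored as minor, the apparent rate would be 2.3% × 0.5 = 1.15% and the risk ratio 0.5, with no true difference.

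A formal test would not separate these patterns from chance. Even at x = 5%, the power of a two-sided 0.05 comparison of 50 against 50 is about 21% or less (normal approximation).

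**Which criteria depend on clinician action.** Both boxes in item 18 do. In item 17 only surgery in the operating room does directly; the hemoglobin criterion needs a test to have been done. Item 17 is therefore less exposed, though not immune.

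**The case against.** The strongest reply is that the AEC already deals with this. It is independent, it includes a hematologist and an intensivist, and bleeding is a listed expected adverse event, so it falls within the committee's remit. That stands, and it narrows the gap to two unstated points: whether the AEC is masked, and whether its category is final.

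The tool is also standardized, with chance-corrected agreement of 0.82. But that figure came from four physicians working blind and independently from the records of 35 children with a bleeding diagnosis. It supports masked review of records more than unmasked site scoring.

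The consequence is limited. The phase 3 rule uses the posterior for CADVT and the dose decision uses ETP. No between-arm test or go/no-go threshold for bleeding is stated, and the 5-event alert is a trial-wide count that prompts the DSMB chair. All of this stands. So does the remark that 2 points per child holds for any binary outcome with 50 per arm: it measures fragility and is not evidence of bias.

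A reader might infer three stronger things that the documents do not support.
- **That reversal is a route into the outcome open only to treated children.** The rescue section says "Protamine may also be used to control the bleeding", but for a bleed that is already clinically relevant, and it does not restrict protamine by arm. UFH is barred only at therapeutic doses, and fresh frozen plasma is also named as an option.
- **That treated children have extra hemoglobin tests.** The Titration dose section only re-times labs already ordered to coincide with the anti-Xa draw. The scheduled blood counts are the same in both arms.
- **That the comparison is known to be biased in one direction.** Nothing establishes this.

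**Conclusion.** The concern holds as a gap in ascertainment. Bleeding severity is classified by assessors who know the arm, partly on a criterion set by clinicians who know the arm. The independent committee that could correct for the assessors' knowledge is not stated to be masked or to have the final say. The between-arm bleeding comparison is open to differential ascertainment; whether any occurs, in which direction and by how much cannot be told from the documents.

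On the protocol's own rates, with 50 per arm, about 0 to 1.5 events are expected per arm and each reclassified child moves an arm by 2 points. The risk ratios in the table rest on an assumed upgrade fraction and show sensitivity only. Reading clinically relevant bleeding as items 17 and 18 together is also an assumption, though it fits the criteria under Discontinuing enoxaparin.

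The efficacy and dose decision rules are not affected. The point is worth acting on because the remedy is cheap and uses a committee that already exists.

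**What to change.** In the AEC section and under Outcome Measures, state that:
1. the AEC assigns the final severity category (tool items 17 to 19) for every recorded bleed in both arms;
2. it works from packets with arm, enoxaparin dosing and anti-Xa results redacted;
3. the AEC category is the reported safety outcome;
4. Major bleeding (item 17) is reported separately from clinically relevant non-major bleeding (item 18).

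Do not redefine medical intervention to exclude drug reversal. That could under-count bleeds in the treated arm and would give the outcome a different meaning from the discontinuation criteria. Instead, the packet should say that a hemostatic intervention was given, without naming an agent that reveals the arm.

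Site-level care, the stopping rules and the real-time DSMB alert stay on the site category, so nothing waits for the committee.

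The cost is protocol and AEC charter wording, redaction of a few packets, and a short delay before the final category is available. Masking will be imperfect. It also cannot undo a clinician's decision to intervene or recover a bleed that the site never recorded, which is the reason for showing item 17 on its own.
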